6.2.6.2. ADA titer

For patients who are ADA ever positive, the maximum observed ADA titer for a patient will be summarized, overall and by ADA subcategories (baseline ADA positive, treatment-boosted ADA, treatment-induced ADA, transient ADA response, persistent ADA response) of patients having each discrete maximum titer value will be tabulated. The denominator to calculate the percentages will be the total number of patients in the associated ADA subcategory.

For patients with treatment-induced ADA, a cross tabulation of duration of ADA response and maximum ADA titer will be provided. The following categories for duration of ADA response will be used: ≤ 1 , >1 to ≤ 3 , >3 to ≤ 5 , >5 to ≤ 7 , >7 to ≤ 13 , >13 to ≤ 16 , >16 to ≤ 25 , >25 weeks. In this categorization, the censoring in duration of ADA response is ignored.

6.2.6.3. Analysis of PK, safety and efficacy by immunogenicity status

The following ADA and nAb status will be used for the analyses described below.

ADA

- ADA ever-positive versus ADA never-positive
- ADA: treatment-induced ADA versus ADA never-positive or baseline ADA positive

nAb

- nAb ever-positive versus nAb never-positive
- nAb: treatment-induced nAb versus nAb never-positive or baseline nAb positive

Data listings will include immunogenicity data together with relevant PK, safety and efficacy data.

PK parameters and immunogenicity status

The following analyses will include patients in both the immunogenicity analysis set and in the PK parameter analysis set. The PK endpoint pertinent to the immunogenicity analyses is C_{trough} .

Blood samples for avelumab PK will be collected pre-dose on Day 1, Day 15 and Day 29 of Cycle 1, on Day 1 and Day 29 of Cycles 2-4, Day 1 of Cycle 6, every 2 cycles after Cycle 6, and 1 month after end of avelumab treatment.

C_{trough} will be summarized descriptively (n, mean, SD, CV, median, minimum, maximum, geometric mean, its associated CV, and 95% CI) by nominal time and ADA status. Linear-linear and log-linear plots of mean and median for C_{trough} over nominal time and by ADA status will be presented.

Among patients with treatment-induced ADA, analyses will be conducted to assess whether C_{trough} has any changes before and after the first positive ADA assessment. To be included in this analysis, patients must have the same PK parameter available both before and after the first positive ADA assessment. Relative PK day will be calculated as:

$$(\text{PK assessment nominal day}) - (\text{first positive ADA assessment nominal day}).$$

Nominal day is the protocol scheduled timing for an assessment. For example, if C_{trough} is collected on Day 1 of Cycle 2 and the first positive ADA result is observed on Day 1 of Cycle 3, then the relative PK day for this C_{trough} is -42. Linear-linear and log-linear plots of mean and median for C_{trough} over relative PK day will be presented.

As data permit, the analyses described above will be repeated for nAb.

Safety and immunogenicity status

The following analyses will include patients in the immunogenicity analysis set.

The frequency (number and percentage) of patients with each of the following will be presented by ADA status.

- TEAEs, by SOC and PT
- TEAEs leading to dose reduction of avelumab, by SOC and PT
- TEAEs leading to discontinuation of avelumab, by SOC and PT

- TEAEs leading to discontinuation of study treatment by SOC and PT
- Grade ≥ 3 TEAEs, by SOC and PT
- SAEs, by SOC and PT
- IRRs, by PT

For patients who had at least one IRR and have treatment-induced ADA, time related to first onset of an IRR (infusion 1, infusion 2, infusion 3, infusion 4 or later) will be summarized taking into account whether the IRR occurred on or after the first ADA positive assessment or whether the IRR occurred before the first ADA positive assessment.

As data permit, the analyses described above will be repeated for nAb.

Efficacy and immunogenicity status

For the ADA ever-positive patients, a listing will be prepared with patient ID, start and stop of avelumab treatment, date of first positive ADA result, time to ADA response, duration of ADA response, date of last ADA positive result, BOR, DR, PFS time or censoring time and reason for censoring, and OS time or censoring time and reason for censoring. If applicable, date of first positive nAb result, time to nAb response, duration of nAb response, date of last nAb positive result will also be presented. Tumor-related endpoints will be presented based on BICR assessment and based on Investigator assessment.

For the ADA ever-positive patients, the percent change from baseline in target lesions as well as the first occurrence of a new lesion and patient off avelumab treatment will be displayed against time point (weeks) in a line plot. Additional symbols will indicate the first and last ADA positive result and, if applicable, the first and last nAb positive result. Plot will be presented separately based on BICR assessment and based on Investigator assessment.

CCI

CCI

CCI

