5.3.1.1. Pharmacokinetic concentrations

Concentrations Below the Limit of Quantification

For all calculations, figures and estimation of individual pharmacokinetic parameters, all concentrations assayed as below the level of quantification (BLQ) will be set to zero. In log-linear plots these values will not be represented. The BLQ values will be excluded from calculations of geometric means and their CIs. A statement similar to 'All values reported as BLQ have been replaced with zero' should be included as a footnote to the appropriate tables and figures.

Deviations, Missing Concentrations and Anomalous Values

In summary tables and plots of median profiles, concentrations will be set to missing if one of the following cases is true:

1. A concentration has been reported as ND (i.e., not done) or NS (i.e., no sample);

2. A deviation in sampling time is of sufficient concern or a concentration has been flagged as anomalous by the clinical pharmacologist.

Summary statistics will not be presented at a particular time point if more than 50% of the data are missing. For analysis of pharmacokinetic concentrations, no values will be imputed for missing data.

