6.2.3. Pharmacokinetic endpoints

The following pharmacokinetic analyses will be based on the PK analyses set.

C_{trough} for avelumab and C_{trough} and C_{max} axitinib will be summarized descriptively (n, mean, SD, CV, median, minimum, maximum, geometric mean, its associated CV, and 95% confidence interval) by cycle and day.

Dose normalized parameters (e.g., CDN- C_{max} , CDN- C_{trough}) will be reported as appropriate. The trough concentrations for avelumab and axitinib will be plotted for each dose (if axitinib is dose titrated) using a box whisker plot by cycle and day in order to assess the attainment of steady state.

Pharmacokinetic parameters for avelumab and axitinib will be taken from observed values or derived from plasma concentration-time data as described in Section 3.2.4.

Presentation of pharmacokinetic data will include:

- Descriptive statistics (n, mean, SD, %CV, median, minimum, maximum) of plasma concentrations will be presented in tabular form by dose level, cycle, day and nominal time. Additionally similar descriptive statistics will also be generated for dose-normalized axitinib pharmacokinetic parameters, if applicable.
- Pharmacokinetic parameters for avelumab and axitinib will be listed and summarized by cycle and study day using descriptive statistics (n, mean, SD, %CV, median, minimum, maximum, geometric mean and its associated %CV, and 95% CI). PK parameters with zero values will be excluded from the calculation of geometric means and its associated %CV. If an inpatient dose escalation or reduction occurs, dose-dependent PK parameters (C_{max}) for that patient may be dose-normalized when it is known that the drug exhibits linear PK within the dose range and other PK parameters will be reported as estimated; or may only be included in descriptive statistics and summary plots up to the time of the dose change. In addition, dose-normalized C_{max} parameters will be

summarized (as described above) using data in which different avelumab and axitinib doses were administered.

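### Plots of avelumab trough against time from first positive ADA cannot, on their own, separate an ADA-related fall in exposure from the rise toward steady state

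*SAP*

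**What the plan says.** SAP 6.2.6.3 takes Ctrough as the PK endpoint for the immunogenicity analyses and specifies two outputs.

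- **By visit and status.** Ctrough is summarised, and its mean and median plotted, by nominal time and ADA status. The status contrasts are ever-positive against never-positive, and treatment-induced against never-positive or baseline-positive combined.
- **By time from onset.** "Among patients with treatment-induced ADA, analyses will be conducted to assess whether" Ctrough "has any changes before and after the first positive ADA assessment". The entry condition is that "patients must have the same PK parameter available both before and after the first positive ADA assessment". The time axis is the nominal day of the PK sample minus the nominal day of the first positive ADA. Mean and median plots "over relative PK day will be presented". The section names no estimate, model, test or rule for attributing a change to ADA.

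Three other places matter. SAP 6.2.3 plots avelumab and axitinib troughs "using a box whisker plot by cycle and day in order to assess the attainment of steady state". SAP 3.2.4, Table 2, defines Ctrough as a pre-dose value under multiple dosing. SAP 5.3.1.1 says that "all concentrations assayed as below the level of quantification (BLQ) will be set to zero".

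**The concern.** Every trough before onset comes from an earlier visit than every trough after it. The Cycle 1 Day 15 sample follows one infusion and the Day 29 sample two. The SAP treats steady state as something still to be shown, so it does not assume that these early troughs are at plateau. Accumulation raises Ctrough over the same weeks in which ADA would lower it, so the bias works against seeing the effect that the plots are meant to reveal.

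Aligning on onset also mixes visits. Relative day −28 is Cycle 1 Day 15 (Day 15) for a patient first positive at Cycle 2 Day 1 (Day 43). It is Cycle 3 Day 1 (Day 85) for one first positive at Cycle 3 Day 29 (Day 113). A first trough and a near-plateau trough then enter the same plotted mean.

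At stake is the reading of one descriptive output under the secondary immunogenicity objective. It is the only Ctrough analysis in the SAP aligned to ADA onset, and it is to be repeated for neutralising antibodies as data permit.

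**Working it through.** **The SAP's own figure.** Nominal day = (cycle − 1) × 42 + day. If a trough "is collected on Day 1 of Cycle 2 and the first positive ADA result is observed on Day 1 of Cycle 3", the days are 43 and 85, and 43 − 85 = −42. This agrees with the SAP.

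**Inputs from the documents.** Dosing every 14 days in 42-day cycles (SAP 6.5.3). Avelumab PK samples on Cycle 1 Days 1, 15 and 29, Days 1 and 29 of Cycles 2 to 4, Day 1 of Cycle 6, then every two cycles (SAP 6.2.6.3). The check runs to Cycle 10 Day 1. Cycle 1 Day 1 is left out, following Table 2.

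**Assumptions.** Half-life of 4 to 14 days, since the documents give none. One compartment, constant clearance, no omitted infusions.

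**Formula.** Let r = exp(−14 × ln 2 / half-life). The trough after n doses, relative to the first trough, is (1 − rⁿ)/(1 − r). The first trough is therefore 1 − r of plateau, and r is the largest fall that accumulation from first trough to plateau can fully hide.

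**Example at 6 days.** r = 0.198. The relative trough is 1.000 at Day 15, 1.198 at Day 29 and 1.238 at Day 43, with a plateau of 1.248. For a first positive at Cycle 1 Day 29, the before value is 1.000. The geometric mean of the ten visits from Day 29 to Day 379 is 1.242, so the ratio is 1.24 with no ADA effect.

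**No ADA effect: geometric mean after / before**

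| Assumed half-life (days) | r | First positive C1D29 | First positive C3D1 |
|---|---|---|---|
| 4 | 0.088 | 1.10 | 1.03 |
| 6 | 0.198 | 1.24 | 1.07 |
| 10 | 0.379 | 1.58 | 1.19 |
| 14 | 0.500 | 1.91 | 1.33 |

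Here the onset visit counts as after. Leaving it out changes little: the largest entry goes from 1.91 to 1.96.

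**True 20% fall from onset.** Each ratio is multiplied by 0.80. For half-lives of 4, 6, 10 and 14 days:

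- First positive at C1D29: 0.88, 0.99, 1.26, 1.53.
- First positive at C3D1: 0.82, 0.86, 0.95, 1.06.

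Dividing by the never-positive after/before ratio over the same visits returns 0.80 in every case. This assumes that never-positive patients accumulate in the same proportion.

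**The companion summary.** If a share p of the ADA group has converted by a given visit, a true 20% fall appears as a ratio of 1 − 0.2p: 0.95 at p = 0.25, 0.90 at 0.5, 0.85 at 0.75, and 0.80 only when all have converted. The effect is diluted but not reversed.

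**The case against.** The strongest reply is that a visit-matched ADA-negative reference already stands in the same subsection, with geometric means and confidence intervals. That is right, and it would be wrong to infer that the SAP has none. At visits by which all treatment-induced patients have converted, that comparison contains no troughs from before their onset. It remains a partial safeguard. At earlier visits it dilutes. The ever-positive group also includes baseline-positive patients, and the treatment-induced contrast puts baseline-positive patients into the reference.

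Second, a reader might infer that accumulation will be credited to ADA, or that the analysis has a high false-positive rate. The documents do not support this. The output is descriptive plots, and a false-positive rate needs a test that the SAP does not specify. A plotted time course also shows more than a single after/before ratio.

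Third, a reader might infer that patients first positive at Cycle 1 Day 15 have a before value of zero, because their only earlier sample precedes any avelumab and BLQ values become zero. Table 2 largely answers this. A sample before the first dose is not a trough under multiple dosing, so these patients have no before value and fail the entry condition. Because SAP 6.2.6.3 lists that sample without comment, confirming the exclusion is still useful.

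Fourth, the size rests on assumed half-life and onset timing. With onset at Cycle 3 Day 1, as in the SAP's worked example, and a half-life of 4 to 6 days, the bias is only 3% to 7%. That stands.

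Population PK modelling could handle accumulation. However, Protocol 9.3.2 and SAP 6.2.4 name no ADA covariate, and the SAP makes the modelling optional.

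**Conclusion.** The point holds as a limit on interpretation. The relative-day plots alone cannot distinguish an ADA-related fall in Ctrough from the rise toward steady state, and the companion summary repairs this only in part. Under the assumed half-lives of 4 to 14 days and no ADA effect, the after/before ratio lies between 1.10 and 1.91 for onset at Cycle 1 Day 29, and between 1.03 and 1.33 for onset at Cycle 3 Day 1. Masking is negligible with a short half-life or late onset. It is large with a long half-life and early onset.

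These figures illustrate the possible bias under the stated assumptions; they do not predict what this trial will show. The analysis is secondary and descriptive, with no decision rule, and it does not bear on the primary PFS and OS tests. The change is a cheap improvement.

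**What to change.** In SAP 6.2.6.3, before aligning on relative PK day, divide each trough by the geometric mean Ctrough of ADA-never-positive patients at the same nominal visit, and plot the ratio. Alternatively, overlay the never-positive reference, matched on nominal visit, on the existing plots. Apply the same step to the nAb version.

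As optional support, fit log Ctrough with nominal visit as a categorical term, a time-varying ADA-positive indicator and a patient random effect.

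Add one sentence confirming that the Cycle 1 Day 1 sample, taken before the first dose, is not a Ctrough, in line with Table 2 in SAP 3.2.4.

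The cost is SAP wording and minor programming on samples already collected. The limitation is that the reference becomes imprecise at late visits if few never-positive patients remain, so their number should be shown at each visit.

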5.2.7. Definition of on-treatment period

Safety endpoints will be summarized based on the on-treatment period unless otherwise specified.

On-treatment period is defined as the time from the first dose of study treatment through minimum (30 days + last dose of study treatment, start day of new anti-cancer drug therapy – 1 day).

Safety data collected outside the on-treatment period as described above will be listed and flagged in listings but will not be summarized.

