6.2.6. Endpoints for immunogenicity data of avelumab

All analyses described below are performed for Arm A only.

Blood samples for avelumab immunogenicity testing will be collected within 2 hours before the start of the avelumab infusion on Day 1, Day 15 and Day 29 of Cycle 1, on Day 1 and Day 29 of Cycles 2-4, on Day 1 of Cycle 6, and then every 2 cycles thereafter. An additional sample must be collected at 30 days after the last dose of avelumab.

Samples positive for ADA will be analyzed for titer and may be analyzed for nAb. As of the finalization of this SAP, the nAb assay is not yet available, therefore the analyses of nAb data described in the following sections will only be conducted contingent upon assay and data availability at the time of reporting.

Patients will be characterized into different ADA categories based on the criteria defined in Table 15.

Table 15 Patients Characterized Based on Anti-Drug Antibody Results (ADA Status)

Category	Definition	Subjects at Risk (Denominator for Incidence)
ADA never-positive	No positive ADA results at any time point; ADA-negative patients (titer < cutpoint)	Number of patients with at least one valid ADA result at any time point
ADA ever-positive	At least one positive ADA result at any time point; ADA-positive patients (titer ≥ cutpoint)	Number of patients with at least one valid ADA result at any time point
Baseline ADA positive	A positive ADA result at baseline	Number of patients with valid baseline ADA result
Treatment-boosted ADA	A positive ADA result at baseline and the titer ≥ 8×baseline titer at least once after treatment with avelumab	Number of patients with valid baseline ADA results and at least one valid post-baseline ADA result
Treatment-induced ADA	Patient is ADA-negative at baseline and has at least one positive post-baseline ADA result; or if patient does not have a baseline sample, the patient has at least one positive past-baseline ADA result	Number of patients with at least one valid post-baseline ADA result and without positive baseline ADA result (including missing, NR)
Transient ADA response	If patients with treatment-induced ADA have (a single positive ADA result or duration between first and last positive result <16 weeks) and ADA result at the last assessment is not positive.	Number of patients with at least one valid post-baseline ADA result and without positive baseline ADA result (including missing, NR)

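### Adverse-event percentages by ADA status ignore time on avelumab, so ADA groups can differ, in either direction, when ADA has no effect

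*SAP*

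**What the plan says.** SAP 6.2.6.3 sets two groupings for Arm A: "ADA ever-positive versus ADA never-positive" and "ADA: treatment-induced ADA versus ADA never-positive or baseline ADA positive". Under Table 15 (SAP 6.2.6) a patient is ever-positive with "At least one positive ADA result at any time point", baseline included. Treatment-induced status depends on post-baseline results. Samples are due on Days 1, 15 and 29 of Cycle 1, then on Day 1 and "Day 29 of Cycles 2-4, on Day 1 of Cycle 6, and then every 2 cycles thereafter", with one more 30 days after the last avelumab dose. Footnote 28 of the protocol's first Schedule of Activities ends the on-treatment samples at Cycle 16.

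For safety, "The frequency (number and percentage) of patients with each of the following will be presented by ADA status". The categories are all TEAEs, TEAEs behind an avelumab dose reduction, TEAEs behind stopping avelumab or study treatment, Grade 3 or higher TEAEs, SAEs and infusion-related reactions (IRRs). SAP 5.2.7 fixes the counting window: "On-treatment period is defined as the time from the first dose of study treatment through minimum" of two dates, 30 days past the last dose and the day before a new anti-cancer drug. The date of the first positive sample plays no part in it.

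Timing relative to ADA is used in two places only. In treatment-induced patients who had an IRR, the infusion at which the first IRR began is summarised "taking into account whether the IRR occurred on or after the first ADA positive assessment" or before it. Ctrough is also compared before and after first positivity. Exposure (SAP 6.5.3) is summarised by treatment arm; no exposure table by ADA status is specified.

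**The concern.** ADA status here is a label earned during follow-up. A patient who leaves avelumab early has few samples and little time to become positive; a patient treated for two years has many samples and much time. The same treatment time gives the second patient a wider window for adverse events. A crude percentage by final ADA label therefore compares groups that differ in exposure by construction.

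If the event itself ends avelumab, the selection works the other way: those patients leave before they can test positive and collect in the never-positive group. Adjacent rows of the same table set could then be biased in opposite directions. A reader could see an ADA-related excess of SAEs that is only longer treatment, or miss a true excess of discontinuations.

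**Working it through.** **No figure to reproduce.** The documents give no ADA incidence, no event rate by ADA status and no expected avelumab exposure. The check is whether the planned count shows a difference when ADA and adverse events are generated independently.

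**From the documents.** With 42-day cycles, the post-baseline sampling days are 15 and 29 (Cycle 1); 43 and 71 (Cycle 2); 85 and 113 (Cycle 3); 127 and 155 (Cycle 4); 5×42+1 = 211 (Cycle 6); then every 84 days: 295, 379, 463, 547 and 631 (Cycle 16). One sample follows 30 days after the last dose. The event window runs to last dose + 30 days. The count is patients with at least one event divided by patients in the group, ever-positive against never-positive.

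**Assumed.** Base case: exponential exposure with median 8 months (cap 30), 15% ADA onset and 40% with the event at 12 months, constant hazards, and the event does not stop avelumab. Exposure medians ran from 6 to 16.9 months, the upper value borrowed from the planned median PFS in SAP 5.1.1. Baseline-positive patients were not modelled. There were 400,000 patients per scenario.

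**Mechanism by hand (base rates, sampling gaps ignored).** ADA hazard = −ln(0.85)/12 = 0.0135 per month; event hazard = −ln(0.60)/12 = 0.0426 per month.
- 3 months on avelumab: P(positive) = 1−exp(−0.0135×3) = 4.0%; P(event), with one month added for the 30-day tail, = 1−exp(−0.0426×4) = 15.7%.
- 18 months on avelumab: P(positive) = 1−exp(−0.0135×18) = 21.6%; P(event) = 1−exp(−0.0426×19) = 55.5%.

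Both probabilities rise with exposure, so they are associated across patients without any ADA effect.

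**Null simulation of the planned count**

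| Scenario | Ever-positive | Never-positive | Ratio |
|---|---|---|---|
| Base case | 49.8% | 32.6% | 1.53 |
| Median exposure 6 months | 43.8% | 27.8% | 1.58 |
| Median exposure 16.9 months | 61.6% | 45.7% | 1.35 |
| Event 10% at 12 months | 14.3% | 8.7% | 1.64 |
| ADA onset spread over 6 months | 39.5% | 34.3% | 1.15 |
| ADA onset within 28 days | 34.5% | 34.9% | 0.99 |
| Event only in first 28 days, not stopping avelumab | 40.1% | 39.8% | 1.01 |
| Everyone treated for 12 months | 42.5% | 42.4% | 1.00 |
| Discontinuation: event always stops avelumab, 15% at 12 months | 11.8% | 13.1% | 0.90 |
| Discontinuation: same, events in first 28 days | 2.4% | 16.1% | 0.15 |

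In the base case median exposure was 16.4 months in ever-positive and 7.0 months in never-positive patients. With ADA able to arise at any time, median treatment of 8 to 12 months and event hazards of 0.03 to 0.08 per month, the ratio was 1.36 to 1.66. With ADA onset limited to the first 2, 3 or 6 months it was about 1.02, 1.06 or 1.14–1.17.

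**Candidate remedies under the null**
- Events after first positivity, as a percentage of all ADA-positive patients, against the never-positive percentage: 19.6% vs 32.6% in the base case, so biased downward. With events confined to the first 28 days it was 0.8% vs 39.8%.
- ADA as a time-dependent status, first events per person-time: rate ratio 0.98 to 1.02 in every constant-hazard scenario. With events clustered in the first 28 days it fell to 0.02–0.22, because nearly all the high-risk time is ADA-negative time.

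The second remedy therefore works only if it also accounts for time since first dose.

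**The case against.** The strongest reply is that these are descriptive tables in one arm. No test, interval or decision rule between ADA groups is planned, SAP 3.5.1 calls safety analyses exploratory, and the immunogenicity paragraph in protocol 9.3.2 commits only to describing ADA frequency, titer, onset and duration. The SAP also lists avelumab start and stop dates and the first positive date for ever-positive patients, summarises time to ADA response, and looks at timing for first IRR onset and Ctrough. Nothing in the documents says ADA arises late; if it arises in the first weeks, the bias is negligible for events spread over treatment.

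Most of this stands, and it limits the weight of the point. It does not remove it. The efficacy listing covers ever-positive patients only, so it gives no comparison. The IRR split concerns when the first reaction began; the IRR frequency table itself is not split.

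Two stronger readings are tempting and should not be drawn. A reader might infer that the fault is counting events that precede positivity. It is not: with equal exposure, 59% of the counted events in positives came before the first positive sample, yet the groups matched at 42.5% and 42.4%. Unequal exposure drives the difference, so the share of earlier events does not measure bias. Baseline-positive patients have no earlier time at all. A reader might also infer that ADA-positive patients will always look worse. The discontinuation rows reverse, and events or ADA onset confined to the first weeks show almost nothing.

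**Conclusion.** The point holds in a limited form. The crude percentages in SAP 6.2.6.3 are open to immortal-time and exposure bias, and no planned table by ADA status would let a reader see or correct it. For events that accrue with exposure and leave avelumab running, the null ratio lies between about 1.0 and 1.66, with differences of roughly 5 to 18 percentage points in the scenarios where ADA onset is spread over months. For events that end avelumab the bias runs downward: slight under a constant hazard (11.8% vs 13.1%), large if they come early (2.4% vs 16.1%).

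These sizes rest on assumed exposure, ADA timing and event rates, and the documents do not favour one end of the range. The tables are secondary, descriptive and confined to Arm A. Nothing here touches the primary endpoints, alpha, sample size or stopping rules.

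**What to change.** In SAP 6.2.6.3:

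1. Show duration of avelumab exposure by ADA status beside the TEAE tables.
2. Add one comparison that respects time, for the listed TEAE categories. Either treat ADA as a time-dependent status, with time and events before the first positive sample counted as ADA-negative, and report exposure-adjusted incidence stratified by time since first dose. Or use a landmark: take ADA status at a fixed early visit among patients still on avelumab and count later events only. Under the null, both compare patients at the same point of treatment.
3. Do not set events after positivity, as a percentage of all ADA-positive patients, against the never-positive percentage, and do not rely on an unstratified person-time rate alone. Both mislead when events come early, and the first does so under a constant hazard too.
4. Repeat for nAb as data permit, since SAP 6.2.6 makes those analyses contingent on the assay.

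The ADA, dosing and event dates needed are already collected, so the cost is programming for a few descriptive Arm A tables. If few patients become positive the strata will be sparse; the landmark version or the exposure table alone may then be all that can be read.
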